10. STUDY CALENDAR

TEST/EVENT	VISITS	
	Pre-Operative visit	Surgery
Informed Consent	X	
Inclusion/Exclusion Criteria	X	
Urine Pregnancy exam	X	
Flourescent dye injection		X
Pathology review		X
Adverse Event Assessment		X

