9. TREATMENT PLAN

a. On-Study Evaluation:

After signing the IRB-approved informed consent form, research participants will be registered by a clinical research associate (CRA) in the Cancer Clinical Trials Office (CCTO). Upon registration, surgery will be scheduled at the next available surgery time slot. All research participants will receive fluorescein injection through their existing intravenous line during their operative procedure for endometrial cancer staging. This will consist of one ampule (5 cc) injected intravenously prior to ligation of the uterine arteries. After the uterus is removed it will be sent to surgical pathology for evaluation as per routine care. The pathologist will open the uterus and evaluate the endometrium. He or she will then cut into the myometrium in an area most suspicious for invasion. The cross section of the myometrium and endometrium will be photographed while exposed to a Woods lamp. The normal myometrium will have a yellow fluorescent appearance under the Woods lamp. The cancerous tissue will have minimal fluorescence. The measurement will be taken estimating the depth of invasion of the cancer into the myometrium on the basis of its physical appearance under the Woods lamp. Cross-sectioning of the uterus is routine procedure by pathology for the intra-operative evaluation of endometrial cancer. This information routinely is provided in order to determine if lymph node staging is necessary.

The area that was measured and photographed will then be prepared for a frozen section to document depth of invasion. This is the standard procedure performed during an endometrial staging. The depth of invasion on the frozen section will be recorded. This same area will undergo histologic confirmation by permanent pathology to determine depth of invasion. The frozen section is part of routine standard of care in evaluation of endometrial cancer.

Subjects will be informed prior to participation in this study that they will have a bright yellow discoloration of their urine and possibly a mild yellow discoloration of their skin for up to 24 hours after the procedure.

b. Dose Assignment: This is a single arm study. A single dose of Fluorescein will be administered to all subjects in this study.

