c. Specimen Handling: The uterus will be sent to pathology immediately after its removal from the patient. The study pathologist will be informed when to expect a subject specimen and will prepare the lab for Woods lamp evaluation, measurement and photography. The remainder of the specimens from the procedure will be processed in the usual manner for routine pathology evaluations.

Visit Breakdown

1. Informed consent will be obtained at the pre-operative surgery appointment.
2. Urine Pregnancy test (only for women of child bearing potential and only if a previous urine pregnancy exam has not been performed within 28 days of consent as standard of care)
3. Injection with the fluorescent dye will occur approximately 5 to 10 min. prior to ligation of the uterine vessels during the hysterectomy.

4. The uterus will be sent to pathology immediately after its removal where Woods lamp evaluation, measurement and photography will be performed.

d. **Prohibited Medications:** none

e. **Dose Limiting Criteria:** none

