11. RISKS AND TOXICITIES TO BE MONITORED

Potential Toxicities, Risks and Precautions

- a. G.I. Nausea can occur in up to 10% of patients however vomiting is uncommon and abdominal pain is rare.
- b. Nervous system. Syncope has been reported between 1 and 10% of patients. There have been very rare reports of convulsions.
- c. Allergic reaction. Hypersensitivity reactions can occur after injection and may be as severe as anaphylaxis. Fatal anaphylactic reaction is reported in 1 of 220,000 angiographies.
- d. Skin. Urticaria and pruitis can frequently occur after injection.

The above side effects will be unlikely to occur given that the injection is done while the patient is under general anesthesia. If there is any evidence of hypersensitivity, the anesthesiologists can utilize antihistamine agents to reduce the duration and severity of the hypersensitivity.

Benefits

There will be no direct benefit to the patient for participation in this study. However, this study may help to identify a less expensive and more rapid method of detecting the extent of endometrial cancer invasion at the time of staging. This could be a benefit in the future for determining which women require lymphadenectomy in which do not.

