Fluorescein and its metabolites are mainly eliminated via renal excretion. After IV administration, the urine remains slightly fluorescent for 24 to 36 hours. A renal clearance of 1.75 mL/min/kg and a hepatic clearance (due to conjugation) of 1.50 mL/min/kg have been estimated. The systemic clearance of fluorescein was essentially complete by 48 to 72 hours after administration of 500 mg fluorescein.

INDICATIONS AND USAGE:

FLUORESCITE® (fluorescein injection, USP) 10% is indicated in diagnostic fluorescein angiography or angioscopy of the retina and iris vasculature.

CONTRAINDICATIONS

FLUORESCITE® (fluorescein injection, USP) 10% is contraindicated in patients with known hypersensitivity to fluorescein sodium or any other ingredients in this product.

WARNINGS

FOR INTRAVENOUS USE

Care must be taken to avoid extravasation during injection as the high pH of fluorescein solution can result in severe local tissue damage. The following complications resulting from extravasation of fluorescein have been noted to occur: Sloughing of the skin, superficial phlebitis, subcutaneous granuloma, and toxic neuritis along the median curve in the antecubital area. Complications resulting from extravasation can cause severe pain in the arm for up to several hours. When significant extravasation occurs, the injection should be discontinued and conservative measures to treat damaged tissue and to relieve pain should be implemented. Rare cases of death due to anaphylaxis have been reported (See [PRECAUTIONS](#)).

PRECAUTIONS

General

Caution is to be exercised in patients with a history of allergy or bronchial asthma. An emergency tray should be available in the event of possible reaction to **FLUORESCITE®** (fluorescein injection, USP) 10%. Use only if the container is undamaged.

Information for Patients

Skin will attain a temporary yellowish discoloration. Urine attains a bright yellow color. Discoloration of the skin usually fades in 6 to 12 hours and usually fades in urine in 24 to 36 hours.

Laboratory Information

If a potential allergy is suspected, an intradermal skin test may be performed prior to intravenous administration, i.e., 0.05 mL injected intradermally to be evaluated 30 to 60 minutes following injection. Given the sensitivity and specificity of skin testing, a negative skin test is not proof that a patient is not allergic to fluorescein.

Carcinogenesis, Mutagenesis, Impairment of Fertility

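### Adverse events are scheduled for assessment only at the surgery visit, with no collection window, so listed effects that need an awake patient may be missed

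*Combined protocol and SAP*

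**What the plan says.** The calendar in section 10 has two columns, pre-operative visit and surgery. The row "Adverse Event Assessment" has one mark, under surgery. The visit breakdown in section 9 stops when the uterus has gone to pathology and been examined there. Neither place has an entry for recovery, discharge or later contact, and no section states when adverse-event collection ends.

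On timing, section 9 says "Injection with the fluorescent dye will occur approximately 5 to 10 min. prior to ligation of the uterine vessels during the hysterectomy". Section 11, whose title announces toxicities to be monitored, includes "Nausea can occur in up to 10% of patients however vomiting is uncommon and abdominal pain is rare" and "Syncope has been reported between 1 and 10% of patients". It then adds: "The above side effects will be unlikely to occur given that the injection is done while the patient is under general anesthesia".

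On how long the dye's effects last, section 9 warns participants of yellow urine and possibly yellow skin "for up to 24 hours after the procedure". The label in Appendix I says "Discoloration of the skin usually fades in 6 to 12 hours and usually fades in urine in 24 to 36 hours" and, under excretion, "The systemic clearance of fluorescein was essentially complete by 48 to 72 hours after administration of 500 mg fluorescein".

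Four other sections bear on the point:

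- Section 12(c) confines the study's data to the pathology results from staging.
- Section 14 names invasion depth by three methods as the endpoints and has no safety endpoint.
- Section 16 requires serious events to reach the principal investigator within 24 hours of becoming known, and all other events to be reported yearly.
- Section 17 plans a quarterly review of adverse and serious adverse events.

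**The concern.** The only scheduled look for adverse events is tied to the visit at which the woman is anaesthetised for the injection. Several of the effects that section 11 sets out to monitor are symptoms she can report only once awake. If staff follow the calendar literally, a nearly empty adverse-event record could mean either that the dye was well tolerated or that nobody asked. The two could not be told apart.

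The quarterly review in section 17 would then rest on incomplete data. The statement in section 11 that side effects are unlikely under anaesthesia would also appear to be confirmed by a record that could not test it.

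**Working it through.** The plan gives no safety figure to reproduce. The check sets the sections side by side and then shows, under a stated assumption, what incomplete capture would do.

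**Step 1. Which listed effects suit an assessment at surgery?** Section 11 names eight effects. The grouping is my reading; the documents do not make it.

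- Need an awake patient: nausea, abdominal pain, syncope, pruritus (4).
- May be masked by anaesthesia: vomiting, convulsions (2).
- Can be seen under anaesthesia: urticaria, hypersensitivity including anaphylaxis (2). Section 11 itself expects the anaesthesiologists to respond to signs of hypersensitivity.

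So 4/8 = 50% clearly need an awake patient, and at most (4 + 2)/8 = 75% are poorly suited to an assessment made under anaesthesia.

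**Step 2. Does another section fill the gap?** Section 16 is not limited to the operation, but it starts only when someone learns of an event, and it gives no end date. It schedules no active collection. Non-serious nausea or itching after waking would be recorded only if someone happened to report it. Section 17 can review only what has been recorded.

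**Step 3. Are the sections consistent?** Read literally, section 12(c) means that no adverse-event data are collected. The calendar has them assessed, section 16 has them reported and section 17 has them reviewed. These cannot all be followed as written.

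**Step 4. Illustration of incomplete capture.** Inputs: n = 100 (section 14, enrolment); p = 10% (the upper figure for both nausea and syncope in section 11) and p = 1% (the lower figure for syncope). The capture fraction c is an assumption, since the documents give none, so the whole range is shown.

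Expected recorded cases = n × p × c. Chance of recording at least one case = 1 − (1 − p × c)^n.

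| c | Expected recorded, p = 10% | Expected recorded, p = 1% | Chance of at least one, p = 1% |
|---|---|---|---|
| 100% | 10 | 1 | 1 − 0.99^100 = 63% |
| 75% | 7.5 | 0.75 | 1 − 0.9925^100 = 53% |
| 50% | 5 | 0.5 | 1 − 0.995^100 = 39% |
| 25% | 2.5 | 0.25 | 1 − 0.9975^100 = 22% |
| 0% | 0 | 0 | 0% |

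The 63% in the first row is the chance that a 1% event occurs at all among 100 women. It does not measure how much is missed.

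**Step 5. Reading a zero.** No recorded cases in 100 women gives a one-sided 95% upper bound of 1 − 0.05^(1/100) = 3.0% on the recorded rate. That bounds the true rate only if capture is complete. At c = 50% the corresponding bound on the true rate is 2.95%/0.5 = 5.9%.

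The direction is clear: any c below 100% lowers the count. The size is not, because c is unknown and p in these anaesthetised women may be below the general figures in section 11.

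**The case against.** The strongest reply is that the calendar does not say adverse events are assessed under anaesthesia. Section 11 says that only of the injection. Surgery is a visit column with no stated hours. It also holds the pathology review, and section 9 has the sampled area go on to permanent pathology after the frozen section. Same-day recovery may therefore fall within it. This stands, and it changes the defect from a window shown to be too short to one that is not defined.

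Two further replies also stand. An effect that anaesthesia prevents has not been missed, so the section 11 rates cannot simply be turned into missed cases. And section 14 plans no adverse-event rate, so no planned analysis is biased.

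A reader might infer more than the documents support:

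- That most listed toxicities cannot be observed. Two of the eight can be seen under anaesthesia, two are a matter of judgement, and section 16 gives a route for events that become known.
- That event rates will be understated, with nearly all cases falling outside the assessment. No onset or capture data support this.
- That the label's 48 to 72 hours sets the required window. It is a pharmacokinetic clearance time, and nothing in the documents says that events arise over that period.

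The existence of section 16 does not answer the central point. A duty to report known events is not a plan to look for them.

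**Conclusion.** The point holds in a limited form. Adverse-event assessment is scheduled only at the surgery visit, nothing schedules it after recovery, and no collection window is defined. Four of the eight effects in section 11, and possibly six, may therefore be missed, and counts may be understated. The amount cannot be derived from the documents; the table shows a range under an assumed capture fraction and is not an estimate.

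Separately, and without any assumption, section 12(c) contradicts the calendar and sections 16 and 17 on whether adverse events are collected at all.

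The conclusion rests on my grouping of the eight effects and on the absence of any other collection instruction. It does not touch the invasion-depth comparison. It is a cheap improvement to the safety data.

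**What to change.** 1. Add a post-operative column to the section 10 calendar with adverse-event assessment taken from the routine recovery and inpatient record, and add the matching line to the visit breakdown in section 9.
2. Define the collection window, covering at least the 24 hours after the procedure over which section 9 itself expects dye effects, and state which hours the surgery column covers.
3. Record onset time relative to injection, and attribution, for each event.
4. Amend section 12(c) so that adverse events are among the data collected, in line with the calendar and sections 16 and 17.
5. As a side point, if the 24-hour notice in section 9 is meant to cover urine as well as skin, reconcile it with the label's 24 to 36 hours for urine. If it covers skin alone, it does not conflict with the label's 6 to 12 hours; say so.

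The cost is a calendar line, a short form and chart review, with no added visit or procedure. The downside is that some recorded events will be due to surgery or anaesthesia. In a single-arm study there is no comparator to separate these, so attribution will rest on judgement and onset time.

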11. RISKS AND TOXICITIES TO BE MONITORED

Potential Toxicities, Risks and Precautions

- a. G.I. Nausea can occur in up to 10% of patients however vomiting is uncommon and abdominal pain is rare.
- b. Nervous system. Syncope has been reported between 1 and 10% of patients. There have been very rare reports of convulsions.
- c. Allergic reaction. Hypersensitivity reactions can occur after injection and may be as severe as anaphylaxis. Fatal anaphylactic reaction is reported in 1 of 220,000 angiographies.
- d. Skin. Urticaria and pruitis can frequently occur after injection.

The above side effects will be unlikely to occur given that the injection is done while the patient is under general anesthesia. If there is any evidence of hypersensitivity, the anesthesiologists can utilize antihistamine agents to reduce the duration and severity of the hypersensitivity.

Benefits

There will be no direct benefit to the patient for participation in this study. However, this study may help to identify a less expensive and more rapid method of detecting the extent of endometrial cancer invasion at the time of staging. This could be a benefit in the future for determining which women require lymphadenectomy in which do not.

12. DATA HANDLING AND RECORD KEEPING

- a. Registration Procedures:** After consent has occurred and eligibility criteria has been completed, subjects must be registered with the CCTO before enrollment to the study. Patients are registered by the Research staff calling the CCTO Office Monday through Friday, 8:00 AM - 4:30 PM. Prior to registration, eligibility criteria must be confirmed by the research staff.
- b. Confidentiality and De-Identification of Data:** Upon registration, the subject will be assigned a unique identifying code or number to which the subject will be identified by. All subject related materials will be identified by that subject's unique identifying code or number. Only the Research staff will have access to the code/number and information that identifies the subject in this study.
- c. Methods for Data Collection and Data Collection Tools:** Data will be entered into OpenClinica through electronic web-based case report forms (CRFs). OpenClinica is a secure open source system for electronic data capture and clinical data management. Data will be stored electronically on encrypted computers. Data collection from this study will be limited to the pathological findings at the time of endometrial cancer staging.
- d. Storage of Study Related Items :** This study's documents will be retained for a minimum of three years after study completion.

13. SPECIMEN STORAGE AND DISPOSAL

Solid tissues will be embedded into paraffin and are stored at room temperature as part of standard pathology evaluation. There will not be a study-specific specimen retained. Photographs of the stained endometrial cancer and myometrium will be retained for purposes of comparison in this study.

14. STATISTICAL CONSIDERATIONS

- a. Sample Size and Study Duration:** 100 subjects will be entered into this pilot study. It is estimated that this study will be completed in less than one year.

- b. Study Endpoints:** Invasion depth as determined using each of three methods: Systemic Fluorescein Injection (SFI), Frozen Section (FS), and Permanent Section (PS).
- c. Data Analysis Plan:** The primary objective is basically to determine whether the SFI method works. Provided that it works, the analysis plan in support of the Secondary Objective is as follows: For each study subject, the paired difference in invasion depths determined using the SFI versus FS methods will be calculated and expressed as a percentage of the FS-based invasion depth. Likewise, the paired difference in invasion depths determined using the SFI versus PS methods will be calculated and expressed as a percentage of the PS-based invasion depth. Each type of paired difference will be summarized as the mean and standard deviation. Because PS is considered the definitive “gold standard” of determining invasion depth, the mean of the paired differences between SFI and PS methods will be compared against equivalence limits of -25% and $+25\%$ via the Two One-Sided Tests (TOST) procedure using an $\alpha=0.10$ significance level. If this mean is significantly “in between” both equivalence limits, then this will indicate that the discrepancy in invasion depths between SFI and PS is significantly less than 25% , and we will accordingly consider further investigation of the SFI method of determining invasion depth.

Sample Size and Power: When two methods are equivalent, the mean of their paired difference will be 0% . The power of the TOST procedure to declare that a mean of 0% is significantly “in between” equivalence limits of -25% and $+25\%$ depends heavily on the standard deviation of the paired difference when the sample size is fixed at 20 subjects. A simulation study using 1,000,000 simulations in PASS 12 software indicates that 20 subjects gives the TOST procedure $>90\%$ power at 10% alpha to declare a mean of 0% to be significantly “in between” the above-stated equivalence limits provided that the standard deviation of the paired differences is less than 37% . This power calculation shows that, if SFI agrees well with PS, then 20 subjects should provide our study with sufficient power to demonstrate that fact.

- d. Missing, Unused and Spurious Data:** Missing data will be treated as missing, and will not be imputed. Spurious data will be corrected at the source document. Any data documented as spurious that is unable to be corrected at the source will be treated as missing.

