2. ABBREVIATIONS

AE – adverse event

CCTO – Cancer Clinical Trials Office

CFR – Code of Federal Regulations

CRA – clinical research associate

CRF – case report form

CTCAE – Common Terminology Criteria for Adverse Events

FDA – Food and Drug Administration

GCP – good clinical practice

IRB – Institutional Review Board

IV – intravenously

mg – milligram

ml - milliliter

PI – principal investigator

PRMC – Protocol Review And Monitoring Committee

RSC – Research Support Center

SAE – serious adverse event

UAMS - University of Arkansas for Medical Sciences

UPIRTSO/UPR – unanticipated problems involving risk to subjects or others

3. **PROTOCOL SUMMARY**

Primary Objective: To determine if Fluorescein systemic injection during hysterectomy procedure can be useful in revealing the depth of endometrial cancer invasion.

Secondary Objectives: To compare depth of invasion as detected with fluorescein to that detected by frozen section and final pathology.

Exploratory Objectives: Can systemic fluorescein injection at time of hysterectomy provide an inexpensive and rapid determination of endometrial cancer invasion into the myometrium.

Study Population: Women with endometrial cancer who are undergoing hysterectomy.

Inclusion Criteria:

1. Known endometrial cancer and scheduled for hysterectomy as part of their treatment.
2. No known allergy to fluorescein dye.
3. Ability to understand and sign informed consent.
4. 18 year of age or older

Exclusion Criteria:

1. Prior hysterectomy.
2. Known sensitivity to fluorescein dye.

Investigational Product: Fluorescein dye injected systemically

Study Design: Pilot

4. **STUDY SCHEMA**

100 women with endometrial cancer who are scheduled for a hysterectomy as a part of their initial treatment

Intravenous injection of 1 ampule (5 cc) of fluorescein dye prior to ligation of the uterine arteries during hysterectomy

Uterus sent immediately to surgical pathology for opening, cross-sectioning, and exposure with Woods lamp to determine depth of invasion of endometrial cancer into the myometrium. Photograph taken of representative area and frozen section performed at same area

Comparison of final pathology depth of invasion with frozen section depth of invasion and fluorescein dye detected depth of invasion to determine accuracy of procedure.

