17. MONITORING

- a. Medical Monitor:** The Medical Monitor, Principal Investigator and study staff will meet quarterly, once the PI has monitored the data, to review safety data (adverse events, serious adverse events and other scientific observations).
- b. Data Monitor:** The study will be monitored by the Principal Investigator to ensure that the rights and well-being of human subjects are protected, that the data are accurate, complete

and verifiable from source documents and that the trial is conducted in compliance with currently approved protocol/amendments.

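### All 100 women are dosed in one stage with no planned check of whether the dye shows the tumour boundary; one non-binding futility look after 20 would limit exposure if the method fails grossly

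*Combined protocol and SAP*

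**What the plan says.** Section 14a states that "100 subjects will be entered into this pilot study", and the schema in section 4 gives the same number: "100 women with endometrial cancer who are scheduled for a hysterectomy as a part of their initial treatment". Section 9b has every participant receive the single dose.

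Section 14c opens with "The primary objective is basically to determine whether the SFI method works" and makes the comparison with frozen and permanent section conditional on a positive answer. It gives no endpoint, threshold, number of women or date for that answer. The one formal test compares the mean percentage difference between fluorescein (SFI) and permanent section (PS) with limits of -25% and +25% "via the Two One-Sided Tests (TOST) procedure using an" alpha of 0.10. No interim analysis is described.

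The power paragraph works with a different number: power "depends heavily on the standard deviation of the paired difference when the sample size is fixed at 20 subjects", and "if SFI agrees well with PS, then 20 subjects should provide our study with sufficient power to demonstrate that fact".

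Section 11 says "There will be no direct benefit to the patient for participation in this study". It notes that hypersensitivity can be as severe as anaphylaxis and puts fatal anaphylaxis at 1 in 220,000 angiographies. Section 17a has a quarterly meeting to "review safety data (adverse events, serious adverse events and other scientific observations"), with no criterion for fluorescein performance.

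**The concern.** In a pilot whose main question is whether a method works, one expects the plan to ask that question before the whole sample is exposed. Here it does not.

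Failure is a realistic possibility on the protocol's own evidence. The Background argues from bowel viability and vulvar Paget's disease, and no title in the Bibliography concerns the uterus or endometrial cancer. The contrast described in section 9a, bright myometrium against poorly fluorescing tumour, is therefore a premise still to be tested.

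The information arrives early. Each specimen is viewed, measured and photographed under the Woods lamp on the day of surgery, and permanent pathology of the same area follows. If most specimens cannot be read, or depth is grossly biased, continuing to 100 gives later women an intravenous agent with no benefit to them and little prospect of a useful result.

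**Working it through.** **1. The plan's own figure.** Inputs from section 14c: n = 20, limits ±25%, true mean 0%, SD 37%, alpha 0.10. Equivalence is declared when mean ± t(0.90, 19 df) × s/√20 lies inside the limits, with t = 1.328 and a true standard error of 37/√20 = 8.27. Exact power is 90.6% (simulation 90.7%), which agrees with the stated figure of more than 90%. At 0.05 per one-sided test it would be 79.5%, so the plan uses 0.10 per test, which corresponds to an 80% confidence interval.

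The 20 is thus a size for showing equivalence when agreement is good. At SD 60% the power with 20 is only 41%, so a failed equivalence test at 20 does not show that the method fails. A look needs its own rule.

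**2. Interval rule at a look after 20.** Stop if the 80% interval for the mean SFI-PS difference lies wholly outside ±25%, that is, if (mean − 25)/(s/√20) > 1.328 or (mean + 25)/(s/√20) < −1.328. The probabilities come from the noncentral t distribution with 19 df and noncentralities (μ − 25)/(σ/√20) and (μ + 25)/(σ/√20). For example, at μ = 50% and σ = 37% the first is 25/8.27 = 3.02, and the stopping probability is 95.3%. SD 37% is the plan's value; SD 60% is an assumption.

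| True mean | SD 37% | SD 60% |
|---|---|---|
| 0% | 0.002% | 0.2% |
| 10% | 0.11% | 0.9% |
| 20% | 3.1% | 5.0% |
| 25% | 10% | 10% |
| 30% | 24.5% | 18% |
| 40% | 69% | 43% |
| 50% | 95% | 71% |
| 60% | 99.8% | 90% |

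With mean 0% and a very large SD (80% or 100%, assumed), stopping is 0.8% or 1.8%. The rule almost never detects large errors that cancel.

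**3. Readability rule.** Stop if 10 or fewer of 20 specimens have a readable boundary: P(X ≤ 10), X binomial(20, p).

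| True readability | Stops |
|---|---|
| 30% | 98.3% |
| 50% | 59% |
| 60% | 24% |
| 70% | 4.8% |
| 80% | 0.26% |
| 90% | below 0.001% |

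**4. Cost to the final test.** Joint simulation of the interval rule at 20 and the equivalence test at 100:

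| True mean, SD | Power without look | Power with look |
|---|---|---|
| 10%, 37% | 99.7% | 99.6% |
| 0%, 60% | 99.6% | 99.4% |
| 10%, 60% | 88.7% | 88.2% |

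A trial stopped at the look makes no equivalence claim, so the false-equivalence rate can only fall.

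**5. Exposure.** 100 − 20 = 80 women remain if the look comes as soon as 20 are dosed. That is a ceiling. Completion within a year means at least 100/4 = 25 women per quarter at even accrual, so a look at the first quarterly meeting would leave about 75 or fewer. Expected anaphylactic deaths in 80 women at the section 11 rate: 80/220,000 = 0.0004.

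**6. Women without a defined percentage.** The difference is a percentage of PS depth, which is undefined at zero depth, and the Background recognises tumours that do not invade the muscle. If only 12 of the 20 have PS depth above zero (assumed), the interval rule at SD 37% stops 83% of the time at mean 50% and 0.4% at mean 10%. The readability rule still uses all 20.

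**The case against.** A case can be made that an interim look in a low-risk, single-dose pilot is optional.

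- **The harm is small.** The dye goes through an existing line, frozen and permanent section proceed as usual, and the stated fatal risk is 1 in 220,000. This stands. The argument for a look is that exposure to a failed method is avoidable, not that it is dangerous.
- **Total failure would be noticed.** No blinding is described, each specimen is seen at surgery, and the section 17a meeting includes other scientific observations. It would therefore be wrong to infer that 100 women are dosed unseen. What is missing is a planned check with a criterion and an action.
- **A reader might infer that 80 women are dosed beyond the number needed.** The documents do not support that. The 20 is the size for equivalence, a secondary objective, at a true mean of 0% and SD below 37%. No number is given for concluding failure, so 80 is only how many would be unexposed at a look after 20.
- **A reader might also infer that 20 specimens would reveal any failure.** They would not. Sections 2 and 3 of the working show reliable stopping only for gross bias or mostly unreadable specimens, and the SD of 37% is the plan's value for a method that agrees well.
- **Readable boundary is not an endpoint in section 14b, and the 10-of-20 threshold is the review's proposal.** True. Both have to be defined before the look can run.
- **The mismatch between 20 and 100 comes first.** If enrolment were reduced to 20 this point would fall away. With 100 confirmed, it remains.

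**Conclusion.** The point holds as a cheap design improvement, not as an error that invalidates the trial. All 100 women are entered and dosed in one stage, the primary question has no criterion or timing, and the existing meeting sets no performance rule.

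A look after 20 protects against gross failure: about 95% or higher probability of stopping at a mean bias of 50% or more with SD 37%, or at about 30% readability, with up to about 80 women then unexposed. If the SD is 60%, the figure at a 50% bias drops to 71%. Moderate failure, and large errors in both directions, will often get through. The chance of stopping a method with mean bias 10% is about 0.1% at SD 37% and 0.9% at SD 60% under the interval rule.

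These figures assume normally distributed percentage differences, 20 analysable women for the interval rule, and independent specimens with a common readability rate. The documents give no evaluable rate and no readability rate.

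**What to change.** Keep the total of 100 and the final equivalence test. Add to sections 14a and 14c:

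- State what it means for the method to work, and record for every specimen whether a fluorescence boundary was readable.
- Hold one non-binding, futility-only look when the first 20 dosed women have SFI and PS results, tabulated at a section 17a meeting.
- Recommend pausing entry if 10 or fewer of the 20 specimens were readable, or if the 80% confidence interval for the mean SFI-PS percentage difference, among women with PS depth above zero, lies wholly outside -25% to +25%.
- Report the SD and the number analysable at the look, because the interval rule does not detect large errors that cancel.
- Allow no early claim of equivalence, so no alpha is spent, and keep the first 20 in the final analysis.

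The authors should also reconcile the 20 in the power paragraph with the 100 to be entered. The cost is protocol wording, one extra data item per specimen and one tabulation at a meeting that already exists, plus the small stopping risk and power loss given above. No extra patients or procedures are needed.
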